5.6 Hypophosphatemia Sub-study Analyses

A separate appendix to this SAP will detail analyses to be conducted in the Hypophosphatemia safety sub-study participants.

5.7 Exploratory Analyses

The below endpoints will be explored to further help interpret the primary analyses. All analyses will be conducted in ITT population only.

- (1) Time to all cause death at one year defined as time from randomization to all cause death within 1 year (non-events censored at 1 year) will be compared using the Cox proportional hazards model.
- (2) Number of heart failure hospitalizations at one year will be analysed using negative binomial regression analysis.
- (3) Combination of all cause death and number of heart failure hospitalizations at one year will be analysed using the same method as used for the primary efficacy endpoint.
- (4) Mean change in the 6MWT distance from baseline to six months will be compared using linear regression adjusting for baseline value of 6MWT distance and region. To assess change from baseline, a baseline measurement and the 6-month measurement both are required
- (5) Time to all cause death through the duration of the study defined as time from randomization to all cause death (non-events censored at last known alive date) will be compared using the Cox proportional hazards model.

- (6) Combination of CV death and total number of heart failure hospitalizations through the duration of the study will be analysed using the same method as used for the primary efficacy endpoint.
- (7) Combination of CV death and total number of urgent heart failure visits through the duration of the study will be analysed using the same method as used for the primary efficacy endpoint.
- (8) Combination of investigator-reported events of cardiovascular death and number of heart failure hospitalizations at 1 year and change in 6-minute walk distance (6MWD) at 6 months using the same method as for the primary efficacy endpoint.
- (9) Time to first investigator-reported cardiovascular death or hospitalization for heart failure will be compared using the Cox proportional hazards model.
- (10) Days alive and out of hospital (any cause) at 1 year as reported by investigator will be summarized overall and by region. It will be compared using a modified Poisson approach.
- (11) Mean change in the 6MWT distance from baseline to 12 months will be compared using linear regression adjusting for baseline value of 6MWT distance and region in the subset of population with NYHA class of III/IV at baseline. To assess change from baseline, a baseline measurement and the 12-month measurement both are required
- (12) Mean change in the 6MWT distance from baseline to 6 months will be compared using linear regression adjusting for baseline value of 6MWT distance and region in the subset of population with NYHA class of III/IV at baseline. To assess change from baseline, a baseline measurement and the 6-month measurement both are required
- (13) Responder analyses for change in 6MWT distance from baseline to 6 months, where a change of 10 and 20 meters respectively is considered as a responder will be tested using chi-square test.

6 SAFETY ANALYSIS

There are no *a priori* hypotheses to be tested for safety. Safety will be assessed within the Safety population unless specified otherwise. Nominal visit-based Box and Whisker plots will be produced for continuous safety variables by randomized treatment where applicable. Shift tables for vital signs will be created for dosing days. Supplementary analyses will only be performed where these summaries suggest that there may be clinically significant differences.

For continuous safety parameters, at least one post-randomization measurement is required for inclusion in the analysis. To assess change from baseline, a baseline measurement is also required.

6.1 Adverse Events (AEs)

In the HEART-FID trial, any adverse experience (AE) that does not meet the definition of SAE is considered non-serious. Non-serious AEs will not be collected for this trial except for AEs leading to cessation of study medication administration. The original term used by investigators to identify non-serious AEs leading to discontinuation of study drug, or the SAEs, will be coded to the Preferred Term level using the Medical Dictionary for Regulatory Activities (MedDRA).

Treatment emergent adverse experiences (TEAE) are defined as those serious or non-serious adverse events that have a start date that is on or after the date of first study medication administration and on or before 30 days from the date of permanent drug discontinuation.

Similarly, treatment emergent serious adverse experiences (TESAE) are defined as those SAEs that have a start date on or after the date of first study medication administration and on or before 30 days from the date of permanent drug discontinuation. Events that have been determined as primary or secondary outcomes in the study are not regarded as SAEs for the safety analysis.

Summary of the following AEs will be provided by treatment group and by System Organ Class (SOC), Preferred Term (PT). These summaries will also be presented overall and by the subgroups of age, sex, race, and body mass index (BMI):

- All AEs (serious or non-serious resulting in discontinuation of study drug)
- All SAEs
- All TEAEs
- All TESAEs
- TEAEs (serious or non-serious) that result in discontinuation of study drug
- TESAEs considered related (possibly, probably or definitely) to study drug
- TESAEs with a fatal outcome.

We will also summarize severity, relatedness, seriousness criteria, and outcome at participant level for All TEAEs, the TEAEs categorized as below, all TESAEs, and All non-serious TEAEs.

TEAEs of Hypophosphatemia by SOC and PT

- MedDRA PT Blood phosphorus decreased
- MedDRA PT Blood phosphorus abnormal
- MedDRA PT Hypophosphataemia
- MedDRA LLT Hypophosphatemic rickets (or Hypophosphataemic rickets)
- MedDRA LLT Rickets familial hypophosphatemic (or Rickets familial hypophosphataemic)
- MedDRA PT Hypophosphatemia osteomalacia

TEAEs of Hypersensitivity/anaphylactoid reactions by SOC and PT

- MedDRA SMQ Anaphylactic reaction (narrow scope)
- MedDRA SMQ Angioedema (narrow scope)
- MedDRA PT of Hypersensitivity
- MedDRA PT of Type II hypersensitivity
- MedDRA PT of Serum sickness
- MedDRA PT of Serum sickness-like reaction
- MedDRA PT of Administration site vasculitis
- MedDRA PT of Type IV hypersensitivity reaction
- MedDRA PT of Stevens-Johnson syndrome
- MedDRA PT of Toxic epidermal necrolysis
- MedDRA Lower Level Term of Type III hypersensitivity reaction
- MedDRA Lower Level Term of Hemolytic anemia drug-induced
- MedDRA Lower Level Term of Haemolytic anaemia drug-induced
- MedDRA Lower Level Term of Immune hemolytic anemia drug-induced
- MedDRA Lower Level Term of Immune haemolytic anaemia drug-induced
- MedDRA Lower Level Term of Drug fever

TEAEs of Injection/infusion site reactions by SOC and PT

- MedDRA HLT Infusion site reactions
- MedDRA HLT Injection site reactions
- MedDRA HLT Administration site reactions NEC
- MedDRA PT Infusion related reaction
- MedDRA SOC of Skin and subcutaneous disorders with a PT of Skin discolourations

TEAEs of Medication error by SOC and PT

- MedDRA SMQ Medication errors (narrow scope)

TEAEs of Hemosiderosis by SOC and PT

- MedDRA PT Haemosiderosis
- MedDRA PT Haemochromatosis
- MedDRA PT Iron overload
- MedDRA PT Hepatic siderosis
- MedDRA LLT Pulmonary siderosis
- MedDRA PT Pulmonary haemosiderosis
- MedDRA PT Superficial siderosis of central nervous system

We will also summarize any non-serious TEAEs occurring in 5 or more percent of participants in any treatment arm. Non-serious AEs as collected for this trial are defined at the beginning of the section.

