1.4. Symptoms and Signs of Hypophosphatemia

Although an FGF23-mediated decrease in serum phosphate after a single infusion of iron is usually transient, the risk of developing clinical symptoms and the actual clinical presentation is determined by the severity of hypophosphatemia and the time to recovery. Management of hypophosphatemia is within the judgment and discretion of the investigator.

Patients with hypophosphatemia typically report bone pain, general weakness, and asthenia [Okada, 1982; Schouten, 2009b; Mani, 2010; Shiraki, 1986; Sato, 1998; Suzuki, 1998; Konjiki, 1994; Shimizu, 2009; Yamamoto, 2013; Moore, 2013; Blazevic, 2014; Fierz, 2014; Vandemergel, 2014; Barea Mendoza, 2014; Poursac, 2015; Sangros Sahun, 2016]. In severe cases, proximal myopathy that also affects the diaphragm and rhabdomyolysis have been reported. The latter can also affect the heart or cause cardiomyopathy or cardiac arrhythmias [Bacchetta, 2012]. Rare manifestations include hemolysis, encephalopathy, seizures [Haglin, 2016]. The type of clinical manifestation expression is also dependent on the age at onset and the duration of hypophosphatemia. Young patients with long-standing hypophosphatemia typically present with growth retardation, delayed dentation and rickets [Elder, 2014]. In adults with hypophosphatemia persisting for several months, long-term complications such as osteomalacia can occur (Fig.2) [Gonciulea, 2017]. Presentation of osteomalacia can include bone pain, fractures, and pseudofractures, which may be difficult to diagnose on conventional X-ray.

Radiological findings are a coarse trabecular structure, and a loss of secondary trabeculae [Phan, 2016]. Low trauma fractures affecting the ribs or scapular "stress-" fractures of the lumbar spine, pelvic structures, and long bones such as femur, tibia, or metatarsal are also common complications of osteomalacia. More sensitive diagnostic tests to identify looser zones, known as 'pseudofractures,' include computed tomography, magnetic resonance imaging, and bone scintigraphy. Bone biopsy showing increased ratio of osteoid to bone surface and reduced tetracycline labeling remains the gold standard for diagnosis, but is rarely performed due to its invasiveness. Although there is

no specific laboratory test for osteomalacia, mildly elevated total and bone-specific alkaline phosphatase in plasma have been repeatedly reported in the context of iron-induced hypophosphatemia [Phan, 2016].

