6.1 Adverse Events (AEs)

The original term used by investigators to identify non-serious AEs leading to discontinuation of study drug, or the SAEs, will be coded to the Preferred Term level using the Medical Dictionary for Regulatory Activities (MedDRA).

The treatment emergent serious adverse experiences (TESAE) are defined as those SAEs that have a start date on or after the date of first study medication administration. Events that have been determined as primary or secondary outcomes in the study are not regarded as SAEs for the safety analysis. Any adverse experience (AE) that does not meet the definition of SAE is considered non-serious. Non-serious AEs will not be collected for this trial except for AEs leading to cessation of study medication administration.

Summary of the following AEs will be provided by treatment group and by System Organ Class (SOC), Preferred Term (PT). These summaries will also be presented overall and by the subgroups of age, sex, race, and body mass index (BMI):

- All AEs (serious or non-serious resulting in discontinuation of study drug)
- All SAEs
- All TEAEs
- All TESAEs
- TEAEs (serious or non-serious) that result in discontinuation of study drug
- TESAEs considered related (possibly, probably or definitely) to study drug
- TESAEs with a fatal outcome.

We will also summarize severity, relatedness, seriousness criteria, and outcome at participant level for All TEAEs, the TEAEs categorized as below, all TESAEs, and All non-serious TEAEs.

TEAEs of Hypophosphatemia by SOC and PT

- MedDRA PT Blood phosphorus decrease
- MedDRA PT Blood phosphorus abnormal
- MedDRA PT Hypophosphatemia
- MedDRA PT Hypophosphatemic rickets
- MedDRA PT Rickets familial hypophosphatemic

TEAEs of Hypersensitivity/anaphylactoid reactions by SOC and PT

- MedDRA SMQ Anaphylactic reaction
- MedDRA SMQ Angioedema
- MedDRA PT of Hypersensitivity

TEAEs of Injection/infusion site reactions by SOC and PT
-MedDRA HLT Infusion site reactions
-MedDRA HLT Injection site reactions
-MedDRA HLT Administration site reactions NEC
-MedDRA PT Infusion related reaction

TEAEs of Medication error by SOC and PT
- MedDRA SMQ Medication errors

TEAEs of Hemosiderosis by SOC and PT
-MedDRA PT Hemosiderosis
-MedDRA PT Hematochromatosis
-MedDRA PT Iron overload
-MedDRA PT Hepatic siderosis
-MedDRA PT Cardiac siderosis
-MedDRA PT Pulmonary hemosiderosis
-MedDRA PT Superficial siderosis of central nervous system

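### The current hemosiderosis adverse-event group has no cardiac term, although SAP v1.0 listed one; a minor gap that one list entry closes

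*Combined protocol and SAP*

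**What the plan says.** SAP v1.3, section 6.1, plans two kinds of adverse-event output.

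- **Overall tables.** "Summary of the following AEs will be provided by treatment group and by System Organ Class (SOC), Preferred Term (PT"). These cover all adverse events, serious events, treatment-emergent events, those leading to discontinuation, and related and fatal serious ones.
- **Participant-level summaries** of severity, relatedness, seriousness criteria and outcome. These are planned for all treatment-emergent events, for the serious and the non-serious ones, and for several named risk groups.

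One named group is headed "TEAEs of Hemosiderosis by SOC and PT". It has seven entries: haemosiderosis, haemochromatosis, iron overload, hepatic siderosis, "MedDRA LLT Pulmonary siderosis", pulmonary haemosiderosis, and superficial siderosis of the central nervous system.

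The corresponding group in SAP v1.0, section 6.1, also has seven entries, including "MedDRA PT Cardiac siderosis".

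Collection is narrow. According to v1.3, "Non-serious AEs will not be collected for this trial except for AEs leading to cessation of study medication administration". What reaches these tables is therefore serious events plus events that stopped the drug.

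**The concern.** The trial gives intravenous iron every six months, as long as re-dosing criteria are met, to patients with reduced ejection fraction. Its iron-overload group names the liver, the lung and the central nervous system but not the heart, the organ whose disease defines the population. The term was in SAP v1.0, so it had once been thought relevant, and nothing in v1.3 explains its absence.

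The participant-level summary for this group is the only planned place where severity, relatedness, seriousness and outcome are tabulated for iron overload as a named risk. The parallel summaries for all treatment-emergent events and all serious ones do not separate iron overload from the rest. If the only iron-overload report were a cardiac one, the group could read zero while the event sat in a long table by preferred term.

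**Working it through.** No power, alpha or event figure is involved, so the check is a comparison of lists followed by a counting argument.

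**Step 1. The two hemosiderosis lists side by side.**

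| Entry | SAP v1.0, 6.1 | SAP v1.3, 6.1 |
|---|---|---|
| Haemosiderosis | yes | yes |
| Haemochromatosis | yes (spelled differently) | yes |
| Iron overload | yes | yes |
| Hepatic siderosis | yes | yes |
| Cardiac siderosis | yes, labelled PT | **no** |
| Pulmonary siderosis | no | yes, labelled LLT |
| Pulmonary haemosiderosis | yes | yes |
| Superficial siderosis of the CNS | yes | yes |
| Total | 7 | 7 |

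One term is lost, one is gained, and six match apart from spelling (7 − 1 + 1 = 7). The pulmonary entry stands where the cardiac one stood.

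**Step 2. Is a reason given?** The version table at the front of SAP v1.3 has no entry for section 6.1, and section 6.1 gives none.

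**Step 3. What one cardiac siderosis event would add.** Take one participant with one such event that is collected and treatment-emergent. Section 6.1 codes events to the preferred term, so the result depends on where MedDRA holds the term.

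| Position of cardiac siderosis in the MedDRA version used | Overall SOC/PT tables | Hemosiderosis group |
|---|---|---|
| Its own preferred term, as v1.0 labels it | 1 | 0 |
| A lower-level term under a listed preferred term | 1, under that term | 1 |
| A lower-level term under an unlisted preferred term | 1, under that term | 0 |

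The group misses the event in the first and third rows and counts it in the second. Section 6.1 names no MedDRA version and the hierarchy is not in the documents, so the row cannot be settled from them.

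**The case against.** There is a good case that little is wrong here.

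- **The dictionary may already cover it.** The v1.0 labels are not fully reliable. Between versions, two rickets terms moved from PT to LLT, and spellings such as that of haemochromatosis were corrected, which suggests a check against MedDRA. Cardiac siderosis may have been removed because it rolls up to a listed term. This stands as a possibility. It does not settle the matter: the rickets terms were kept at their new level, whereas the cardiac term was kept at none.
- **The change log proves little.** It claims to list only major changes and clarifications. It also omits other edits to section 6.1, such as the longer hypersensitivity list and the 30-day limit on treatment emergence. SAP v1.0 is superseded, so differing from it is no contradiction. This stands. A reader might infer an undisclosed or mistaken deletion, but the documents show only that the term is absent and unexplained.
- **Nothing collected disappears.** A reader might infer that a cardiac siderosis event would go uncounted altogether. It would not, because the overall tables by system organ class and preferred term do not depend on the groups.
- **The operative lists may be elsewhere.** The SAP refers to a supplemental appendix of definitions and to separate table specifications, neither of which is available. The term could be there, but section 6.1 as written does not include it.

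**Conclusion.** The gap is real in the text of SAP v1.3 and its size is minor. As written, an event coded to a cardiac siderosis preferred term adds nothing to the grouped iron-overload summary, although it remains in the overall tables. This rests on one assumption, that cardiac siderosis does not roll up to a listed preferred term in the MedDRA version used. If it does, the group counts it and only a clarifying word is needed.

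The documents give no rate, so the number of events at stake cannot be estimated. The planned cumulative iron dose does not help, since it says nothing about how many events the group would miss.

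A reader might infer a matching gap in the hypophosphatemia group, whose only osteomalacia entry is "MedDRA PT Hypophosphatemia osteomalacia". The documents do not support treating that as a defect. Plain osteomalacia was in neither SAP version, and v1.3 widened the group by adding the cause-specific form. The sub-study appendix, section 1.4, says in background text only that "long-term complications such as osteomalacia can occur". Restricting a hypophosphatemia group to the cause-specific term is a defensible choice between specificity and sensitivity.

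**What to change.** In SAP section 6.1, put cardiac siderosis back in the hemosiderosis group, at the PT or LLT level at which the MedDRA version in use holds it, and state that version. If the term was dropped because it rolls up to a listed preferred term, say so in one sentence instead.

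The cost is one list entry. It needs no new data and has no effect on alpha or on any efficacy analysis. Section 10 of SAP v1.3 allows further appendices to be finalised before database lock, so the entry could also be made there.

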6.2 Laboratory Data

- Descriptive statistics at baseline and at each scheduled (or reported) visit through 1 year along with the lowest observed value and the highest observed value will be provided for central laboratory measurements as identified below, and for changes from baseline by treatment. Shift tables will be provided for the max or min changes relative to baselines. Grades based on Common Terminology Criteria for Adverse Events (CTCAE) version 4.0 or higher will be identified algorithmically where possible and as applicable for Haematology and Chemistry central laboratory data and they will be summarized by scheduled visit through 1 year using bar-chart and percentages. Any subjects with missing baseline values will not be included in change from baseline or shift tables
 - a. Hematology: Hb, Hct, RBC, WBC, MCV, MCH, MCHC, RDW, platelets, differential count, and reticulocyte count
 - b. Chemistry: Sodium, potassium, chloride, BUN, creatinine, eGFR (calculated using CKD-EPI formula), albumin, alkaline phosphatase, total bilirubin, GGT, AST, ALT, LDH, calcium, phosphorus, glucose, bicarbonate, serum glucose, albumin and magnesium
 - c. Iron indices: Serum iron, serum ferritin, total iron binding capacity (TIBC), percentage serum transferrin saturation (TSAT), and Unsaturated Iron Binding capacity
 - d. Other: 1,25 (OH)₂ Vitamin D, 25 (OH) Vitamin D, Parathyroid Hormone as collected in sub-study participants, NT-proBNP

Additionally, Hb and iron indices laboratory data will be summarized in ITT population too.

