Initial treatment will occur on Day 0 (date of randomization) and Day 7. On Day 0 and Day 7, Group A (FCM) will receive a 750 mg undiluted blinded dose of IV FCM at the rate of approximately 100 mg (2 mL)/minute; Group B (placebo) will receive a blinded placebo (15 cc of normal saline) IV push at 2 mL/minute. Participants in Group A with body weight <50 kg (110 pounds) will have individual FCM doses adjusted to 15 mg/kg, not to exceed an individual dose of 750 mg, or a cumulative dose of 1500 mg per treatment cycle.

All participants will be dosed every 6 months for the duration of the trial. Participants randomized to the FCM arm will be dosed as indicated based on hemoglobin (Hgb) levels (i.e. Hgb <13.5 g/dl [females] or <15.0 g/dl [males])) and iron studies (i.e. serum ferritin <100 ng/mL or 100 to 300 ng/mL with TSAT <20%). Participants not meeting post- randomization lab criteria for blood counts and iron studies and all participants randomized to the placebo arm will be administered IV placebo at each visit.

Unblinded site personnel, responsible for preparation and administration of the FCM or Placebo, will ensure that the participant and all blinded site staff are not able to observe the preparation or administration of study treatment.

**Patient
Assessments**

Efficacy and Safety Follow-up: All participants will be followed from the time of randomization until completion of the trial. The last participant randomized will be followed for 12 months. After treatment on Day 0 and Day 7, participants will be evaluated at 3 month intervals (in person or via telephone), with additional dosing administered every 6 months as applicable (see Section 3.1). Hematology, ferritin, and transferrin saturation (TSAT) laboratory assessments will be performed in all participants, with appropriate safety evaluations, to determine if additional treatment will occur at 6 month intervals. At the conclusion of the study all participants will be assessed for the occurrence of any potential endpoint or serious adverse events. Attempts to determine Vital Status, including endpoint ascertainment, for participants who are lost to follow-up or withdrawn will be made via a search of available public records, and other appropriate investigative techniques, including the potential use of third party vendors as described in the informed consent form and in accordance with applicable regulatory requirements.

**Primary
Endpoint:**

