1.4 Sample Size and Power

The study design allows for sufficient power for both the primary and top secondary outcomes. Numerical simulations based on multivariate normal vectors ([Appendix 2](#)) were conducted to estimate power for the primary treatment comparison based on the following assumptions about events rates described in **Table 1.4.1**

Table 1.4.1. Assumptions about Event Rates for Primary Outcome

Ranked tier at 12-month endpoint (6 month for 6 MWT)	Control	Treatment
Death total	8%	6.8%
Death without hospitalization	4%	3.4%
Death with hospitalization	4%	3.4%
Hospitalizations in survivors		
1	6%	4.8%
2	3%	2.4%
3 or more	1%	0.8%
Change in 6 Minute Walk Test	Mean = 0 SD = 90	Mean = 18 SD = 90

With 3014 participants (1507 per arm) and 2.5% annual loss to follow-up for clinical outcomes and 15% of individuals with missing 6MWT at 6 months (unable to perform or lost to follow-up), projected simulations estimate 90% power at an overall two-sided significance level of 0.01, accounting for one interim analysis as described in [Section 7.1](#).

For the top secondary composite, there is an assumed event rate of 0.0128 per month in the control arm which represents conservative 75% discounting of the event rate obtained by the FCM meta-analysis [[Anker 2015](#)]. The anticipated hazard ratio (HR) was set at 0.80 (20% reduction). Uniform enrollment was assumed over the period of 30 months, with an anticipated minimum follow-up of 12 months (required minimum of 6 months), anticipated maximum follow-up of 42 months (no required maximum), and monthly loss to follow-up of 0.0021 (2.5% annualized). With these assumptions, 1500 per study arm (3000 total) provides 90% power to reject the null hypothesis of no difference between treatment arms when tested at an overall two-sided level of significance $\alpha=0.05$, accounting for one interim analysis as described in Section 8.10 of the CSP. This results in a total of 771 participants with events (in case of multiple events experienced by a participant, only their first one will be counted towards the 771) necessary to achieve the desired power. Thus, the trial has the potential opportunity to be stopped at a point where the projected number of participants reaches 771 events, but no earlier than the last participant reaching 12 months of follow-up.

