6.4 Vitals and Physical Assessments

- Descriptive statistics and change from baseline by treatment at each scheduled visit will be provided through 1 year along with the worst observed value and the best observed value targeted physical exam results and vital signs (pre-dose, post-dose and

30 min post-dose) and: systolic blood pressure (SBP), diastolic blood pressure (DBP), heart rate, and BMI.

- Shift tables for Heart rate, SBP and DBP will be provided for the dosing days through 1 year. Baseline for these shift tables will be the pre-dosing value at the respective visit.

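### SAP v1.3 stops the by-visit laboratory, CTCAE-grade and vital-sign tables at 1 year, although dosing and these measurements continue every 180 days to end of study

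*Combined protocol and SAP*

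**What the plan says.** **Tables limited to 1 year (SAP v1.3).**
- Section 6.2, laboratory values: "Descriptive statistics at baseline and at each scheduled (or reported) visit through 1 year".
- Section 6.2, CTCAE grades: "they will be summarized by scheduled visit through 1 year using bar-chart and percentages".
- Section 6.4, vital signs: "Descriptive statistics and change from baseline by treatment at each scheduled visit will be provided through 1 year".
- Section 6.4, dosing days: "Shift tables for Heart rate, SBP and DBP will be provided for the dosing days through 1 year".

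**Treatment and measurement continue.** The final protocol's synopsis states: "All participants will be dosed every 6 months for the duration of the trial". The schedule in protocol section 3.3 repeats the follow-up visits every 180 days until the study ends. Section 6.4.2 places a central hematology, chemistry and iron-index draw 4 to 20 days before each repeat course, and vital signs are taken before and after every dose. Section 6.4.3.1 lists first-dose visits out to Day 1,080 and on to end of study. SAP v1.3 section 1.4 gives an "anticipated maximum follow-up of 42 months".

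**Outputs with no 1-year limit of their own.** Treatment-emergent adverse events (6.1) run until 30 days after permanent discontinuation. Exposure and redosing-threshold rates are in 6.5, and nominal-visit box plots are in the opening of section 6. Section 6.2 also plans shift tables on maximum or minimum change. Lowest and highest laboratory values are planned ("along with the lowest observed value and the highest observed value will be provided"), but whether they cover all follow-up or only year 1 is not said. The same is true of the worst and best vital-sign values in 6.4.

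**The concern.** Repeated intravenous iron over two to three years is the part of the safety profile that this trial is well placed to describe. Iron accumulation (ferritin, TSAT), liver tests, phosphorus and infusion-day blood pressure are the measurements that bear on it, and they are collected at every cycle. Under the plan as written, a grade 3 or 4 laboratory value in year 2 or 3 enters no specified grade table, and a dosing-day blood-pressure shift in year 2 or 3 enters no specified shift table.

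The adverse-event tables cannot fill this gap. Non-serious events are collected only if they lead to stopping study drug (protocol 7.2, SAP 6.1), so a silent laboratory change would be seen mainly in the laboratory data. The phosphate sub-study does not fill it either, because it follows the initial course only (protocol Appendix 1, section 3.2).

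**Working it through.** **1. Reproduce the plan's follow-up assumption.** From SAP v1.3 section 1.4: 30 months' uniform enrollment plus 12 months' minimum follow-up gives 30 + 12 = 42 months. As a cross-check, take monthly event rates of 0.0128 (control) and 0.80 × 0.0128 = 0.01024 (treatment), monthly loss of 0.0021, follow-up uniform on 12 to 42 months, and 1507 per arm. For event rate λ and loss η, the expected event proportion is the average over u from 12 to 42 of λ/(λ+η) × [1 − exp(−(λ+η)u)]. This gives 0.2797 and 0.2317, so 1507 × (0.2797 + 0.2317) ≈ 770.8 events. The plan states 771, so the assumption is reproduced.

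**2. Person-time after month 12.** Add mortality of 0.0066 per month. This is an assumption, close to the 8% control-arm annual death rate in Table 1.4.1 (8%/12 = 0.0067). Total attrition is h = 0.0021 + 0.0066 = 0.0087 per month.
- Expected time in the first 12 months: (1 − exp(−12h))/h = 11.4 months.
- Mean total: (1/h) × [1 − (exp(−12h) − exp(−42h))/(30h)] = 23.8 months.
- Share after month 12: 1 − 11.4/23.8 = 52%.
- With no attrition: mean 27.0 months and share 15/27 = 56%.

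**3. Planned courses.** A course at month m is reached by a fraction exp(−hm) × G(m), where G = 1 up to month 12 and (42 − m)/30 after that.

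| Month | exp(−hm) | G | Courses per participant | Per arm (×1507) |
|---|---|---|---|---|
| 0 | 1.000 | 1.0 | 1.000 | 1507 |
| 6 | 0.949 | 1.0 | 0.949 | 1430 |
| 12 | 0.901 | 1.0 | 0.901 | 1358 |
| 18 | 0.855 | 0.8 | 0.684 | 1031 |
| 24 | 0.812 | 0.6 | 0.487 | 734 |
| 30 | 0.770 | 0.4 | 0.308 | 464 |
| 36 | 0.731 | 0.2 | 0.146 | 220 |

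- Months 0 to 12: 2.85 courses. Months 18 to 36: 1.63. Total: 4.48.
- After month 12: 1.63/4.48 = 36%.
- On the 180-day grid, with visits omitted within 30 days of the end-of-study visit, the total is about 4.4 courses and the later share is again 36%. Without attrition these become 4.9 and 39%.

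**4. Which courses each table reflects.** The pre-dose draws in year 1 fall at about Days 160–176 and 340–356, after courses one and two. The next scheduled pre-dose draw, at about Days 520–536, is the first after the Day 360 course. By-visit laboratory tables therefore reflect the first two courses: (1.000 + 0.949)/4.48 = 44% of planned cycles. Vital-sign shifts use the same visit's pre-dose value as baseline, so the Day 360 course counts: 2.85/4.48 = 64%. This is slightly generous, because the second dose of that course is scheduled for Day 367.

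**The case against.** A reader might infer that repeat-dosing safety goes unreported. The documents do not support that.
- The Day 180 course lies inside the 1-year tables, as does the Day 360 course for vital signs.
- The adverse-event tables are not cut at 1 year, and they include groupings for hypophosphatemia, hypersensitivity, infusion-site reactions and iron overload.
- Section 6.5 reports cumulative dose, and the proportion of participants outside the redosing thresholds before any dosing visit.
- The laboratory shift tables and the box plots state no limit.

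Nor can one say that only each participant's lowest and highest laboratory values survive beyond year 1, or that late hemoglobin and iron separation is unreported. The sentence in 6.2 adding hemoglobin and iron indices for the ITT population states no cut of its own.

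It is also fair to say that safety carries no prior hypotheses and that no efficacy estimate or test is affected. ICH listings are planned, the DSMB reviews safety data at least every 6 months, and the table specifications sit in separate documents not available here. Planned cycles overstate active ones, because FCM-arm participants who do not meet the laboratory criteria receive placebo at that cycle.

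All of this narrows the point, but a gap remains. Box plots are promised only where applicable and give no counts or grades. Maximum and minimum shifts do not show when, or after how many courses, a change occurred. Listings do not summarize by arm. End-of-study visits also include central laboratory samples, but for participants who received the Day 360 course these too fall after year 1. Separate specifications could add tables, but the SAP's stated rule is the 1-year limit.

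**Conclusion.** The concern holds in a limited form. Laboratory values and CTCAE grades after the third and later courses, and dosing-day vital-sign shifts after year 1, are not tabulated by visit or grade. The window for the extremes and the laboratory shift tables is undefined. This is a stated rule in the SAP, not a missing detail.

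About 52% of planned person-time and 36% of planned cycles lie outside these tables, or 56% and 39% without attrition. The figures rest on uniform follow-up over 12 to 42 months, the plan's loss rate and an assumed mortality of about 8% a year. Forty-two months is an anticipated maximum, not a cap, and the mean is about 24 months. The number of active FCM courses after year 1 is smaller than the planned count by an amount the documents do not give.

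**What to change.** 1. In SAP sections 6.2 and 6.4, replace the 1-year limit with every scheduled visit through end of study, subject to a minimum number per arm. Fifty is a workable example, chosen for illustration. The month 36 column would hold about 220 per arm under the assumptions above. Keep the 1-year table as the headline.
2. Add a table of the worst CTCAE grade at any time after baseline, by arm.
3. State that the lowest and highest laboratory values, the worst and best vital-sign values, and the laboratory shift tables use all post-baseline data.
4. State the same window for the ITT hemoglobin and iron-index summary.

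No new data are needed and alpha is untouched. The cost is longer tables. Late columns will be sparser and restricted to participants who were enrolled early and survived, so they should carry their denominators and be read as descriptive.
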